### 2.1.3.2 Legally marketed device:

- Software version: 10 X
- Datex-Ohmeda respiratory gas module: M-CAIOVX, M-CAIOV, M-CAIO, E-CAIOVX, E-CAIOV, or E-CAIO

### 2.1.3.3 Investigational device:

- Model: Aisys CS
- Software version: 10 X with Et Control Option;
- With Fresh Gas Module (FGM) hardware

### 2.1.4 Traceability of the Investigational Device:

Each investigational Et Control option kit (including installation instructions, user reference manual, and hardware) is serialized.

In addition, unique serialized investigation warning labels will be affixed to the Aisys CS each time the investigational Et Control option is enabled for the study subject and removed when the Et Control option is disabled. These activities along with the serialized investigation warning labels and the serial number of the legally marketed Aisys CS will be recorded along with the subject ID in the Device Accountability Checklist/Log.

### 2.1.5 Intended Use of the Marketed Aisys CS Device:

The GE Datex-Ohmeda Aisys CS Anesthesia System is intended to provide general inhalation anesthesia and ventilatory support to a wide range of patients (neonatal, pediatric, and adult). The device is intended for volume or pressure control ventilation. The Aisys CS is not suitable for use in an MRI environment.

### 2.1.6 Indications for Use of the Investigational Device:

The investigational Et Control option is designed to support clinicians in maintaining the targeted end tidal oxygen and end tidal anesthetic agent concentrations that the clinician sets during an anesthetic procedure by making multiple, limited adjustments to the fresh gas composition and total flow. The Et Control option is indicated for adult patients, 18 years of age and older.

### 2.1.7 Description of Materials that May Come into Contact with Tissues or Body Fluids:

The investigational Et Control option consists of a fresh gas module (FGM) inserted onto the Aisys CS, to periodically multiplex the fresh gases to the gases being sampled by the respiratory gas monitor. Gases sampled by the respiratory gas monitor are evacuated. The FGM modules for the investigational Et Control option does not contact the patient, tissues or body fluid as sample gas is not returned to the breathing system. No new materials are

**Study Title:** Multi-site Anesthesia randomized controlled Study of End tidal control (Et Control) compared to conventional anesthesia Results (MASTER-Anesthesia Trial)  
**Study No:** 123.07-2015-GES-0002

GE Healthcare

introduced that are in contact with the patient. The gas pathway materials of the Aisys CS device remain unchanged as cleared in K132530.

### 2.1.8 Summary of Training and Experience Required to Operate the Investigational Device:

Clinicians that participate in the clinical trial have proficiency in the delivery of general anesthesia and prior operational experience with the legally marketed Aisys or Aisys CS. The description of the legally marketed device is found in the Aisys CS User's Reference Manual Software Revision 10.X, #2067226-001. The URM will be provided to all clinicians who participate in the trial.

Training in the use of the Et Control option is described in Section 7.2, Training Plan for Research Device. Et Control instructions for use are included in Aisys CS Et Control Option Addendum Software Revision 10.X URM #2070086-001 that has been revised to include the Investigational User label on each page. This document will be provided to all clinicians involved in the study.

### 2.1.9 Device Import/Export Requirements:

No investigational devices will be imported into the US or exported out of the US. All research sites will be located in the US.

## 2.2 Regulatory Status

The Aisys CS anesthesia device, upon which the investigational Et Control option will operate, is a legally marketed device under K132530.

The Datex-Ohmeda respiratory gas modules (M-CAIOVX, M-CAIOV, M-CAIO, E-CAIOVX, E-CAIOV or E-CAIO) are legally marketed devices under K001814, K051092. The Fresh Gas Module (FGM) hardware is investigational.

The investigational Et Control option is pre-market with an Investigational Device Exemption (IDE) required for clinical trials in the US.

## 2.3 Risk Category/Rationale

The investigational Et Control option is an optional feature of a life support system and is therefore a significant risk device.

## 2.4 Device Classification and Rationale

The legally marketed Aisys CS anesthesia machine is an anesthesia system classified as a Class II medical device in 21 CFR 868.5160. The product code is BSZ.

**Study Title:** Multi-site Anesthesia randomized controlled Study of End tidal control (Et Control) compared to conventional anesthesia Results (MASTER-Anesthesia Trial)  
**Study No:** 123.07-2015-GES-0002

GE Healthcare

Aisys CS, with the investigational Et Control option, remains a Class II medical device with the same classification.

The legally marketed Datex-Ohmeda respiratory gas modules (M-CAIOVX, M-CAIOV, M-CAIO, E-CAIOVX, E-CAIOV or E-CAIO) are classified as Class II gas analyzers under 21 CFR 868.1400 or 868.1720 with primary product codes of CCK or CCL respectively.

## 2.5 Device/Product Issuance and Replacement

### 2.5.1 Device Issuance and Replacement – Site -Owned Equipment

For an enrolled subject in the Et Control Arm, the Et Control software feature will be activated by a trained site technician, the Fresh Gas Module will be attached, and Et Control investigational labeling will be attached. When these actions are completed, the site's Aisys CS is classified as an investigational device, and may not be used on a subject, who is not enrolled in the clinical trial.

Upon completion of anesthesia case in the Et Control Arm, the trained site technician will deactivate the Et Control feature, uninstall the hardware, verify that the Aisys CS is reversed to its cleared device state, and finally remove and affix the investigational labels onto the Device Accountability Checklist/Log. These actions confirm that the site's Aisys CS is no longer an investigational device; and may be used for a clinical patient, who is not enrolled in the research study.

For an enrolled subject in the Control Arm, the Et Control option will not be activated; the anesthesia case is conducted using a site Aisys CS device cleared to be used for a clinical patient.

Upon completion of each research subject's surgery, a trained site technician will retrieve the electronic Aisys CS data log.

It is anticipated that the transition from a non-investigational device to an investigational device and back again to a non-investigational device will take place more than once each day during the enrollment period. Tracking of these transitions and documenting the correct configuration for each research subject will be the responsibility of investigator or designee. The investigational device accountability checklist/log, which will be maintained by the investigator or designee, will provide a duplicate tracking mechanism to ensure accuracy and control of the use of the investigational device.

### 2.5.2 Maintenance and Storage

The investigational devices shall be clearly labeled per 21CFR 812.5: **CAUTION- Investigational device. Limited by Federal law to investigational use.** The investigational Et Control option, consisting of the FGM, will be located in a secured location at the investigational site under the supervision of the Principal Investigator.

**Study Title:** Multi-site Anesthesia randomized controlled Study of End tidal control (Et Control) compared to conventional anesthesia Results (MASTER-Anesthesia Trial)  
**Study No:** 123.07-2015-GES-0002

GE Healthcare

The Sponsor may provide the Aisys CS2 device(s) to the participating investigational site for use in this clinical study, if not available. The site-owned Aisys CS may be provided with airway gas module, if not available.

## 2.6 Disposition of the Device (including software version) and related materials (e.g. accessories, supplies, consumables)

The investigational Et Control option, consisting of the FGM, will be removed and returned to the Sponsor upon completion of the study. The legally marketed device, Aisys CS anesthesia machine, which is owned by the investigational site, will remain as property of the site. If the site is provided an Aisys CS anesthesia machine it may be returned to the Sponsor upon completion of the study.

## 3. OBJECTIVES OF RESEARCH STUDY

### 3.1 Purpose of the Study

The purpose of this pivotal study is to:

- (1) demonstrate that End tidal Control (Et Control) performance is non-inferior to conventional anesthesia practice in an adult surgery population, AND
- (2) support a marketing application in the U.S. for clearance of this feature.

### 3.2 General Design of Study (Descriptive Hypothesis)

This clinical study has been designed to compare the performance of the Et Control Arm (investigational arm) to the Control Arm (fresh gas mode). This is to demonstrate that the performance of the Et Control is non-inferior to the conventional anesthesia practice in an adult surgical population. A total of 248 subjects scheduled to undergo general anesthesia will be enrolled in the study. Subjects will be randomized to either the Et Control Arm or the Control Arm at a 1:1 ratio. Stratified randomization will be used based on Investigator, subject's pre-existing hypertension status, and subject's ASA status.

### 3.3 Study Objectives

#### 3.3.1 Primary Objective:

The primary objective is to demonstrate that End-tidal Control (Et Control) achieves and maintains the concentration of end-tidal anesthesia agent (EtAA) and the concentration of end-tidal oxygen (EtO2) in a manner that is non-inferior to conventional anesthesia practice by a margin of 5% in an adult surgery population.

The hypotheses for the primary endpoints are:

$$H_0: \mu_{\text{Et}} - \mu_{\text{con}} < -5\% \text{ vs } H_1: \mu_{\text{Et}} - \mu_{\text{con}} \geq -5\%$$

**Study Title:** Multi-site Anesthesia randomized controlled Study of End tidal control (Et Control) compared to conventional anesthesia Results (MASTER-Anesthesia Trial)  
**Study No:** 123.07-2015-GES-0002

GE Healthcare

for both EtAA and EtO2, where  $\mu_{et}$  is the average percent duration of Et Control with EtAA and EtO2 maintained within the acceptable range, and  $\mu_{con}$  is the average percent duration of control device with EtAA and EtO2 maintained within the acceptable range.

### 3.3.2 Secondary Objective:

The secondary objectives are to:

- (1) gather additional functional and safety data in clinical use of the investigational Et Control option.
- (2) gather data on the amount of inhaled anesthetic agent and gas used in the Et Control Arm versus the Control Arm.

The hypothesis for the anesthetic agent usage is:

$$H_0: \mu_{et} - \mu_{con} = 0 \text{ vs } H_1: \mu_{et} - \mu_{con} \neq 0$$

where  $\mu_{et}$  is the average normalized anesthetic agent usage of the Et Control arm, and  $\mu_{con}$  is the average normalized anesthetic agent usage of the control arm.

- (3) obtain data on the number and frequency of user interactions with the Aisys CS user interface in the Et Control Arm versus the Control Arm.

The hypothesis for the user setting interaction for the duration from induction to the end of anesthesia is:

$$H_0: \mu_{et} = \mu_{con} \text{ vs } H_1: \mu_{et} \neq \mu_{con}$$

where  $\mu_{et}$  is the median of user setting interaction of the Et Control arm, and  $\mu_{con}$  is the median of user setting interaction of the control arm.

- (4) collect time to discharge from the operating room (OR), which is measured from the time of end of surgery (*often defined as procedure end time, last stitch, or placement of last bandage*) to time of last breath.

## 3.4 Study Endpoints

### 3.4.1 Primary Endpoint:

- (1) Percent duration without large deviation of EtAA:

Percent duration of EtAA concentration during steady state maintained within the acceptable limit, which is defined as the greater of 5% of the steady state inhaled anesthetic agent concentration and 0.6% v/v for Desflurane (Des), 0.2% v/v for Sevoflurane (Sev), or 0.1% v/v for Isoflurane (Iso). The percent duration is the weighted average of all steady states for a subject, using the duration of steady state as the weight. It is expressed as:

**Study Title:** Multi-site Anesthesia randomized controlled Study of End tidal control (Et Control) compared to conventional anesthesia Results (MASTER-Anesthesia Trial)  
**Study No:** 123.07-2015-GE5-0002

GE Healthcare

$$PercentDuration = \frac{\sum_j \sum_i t_{ij} I_{ij}}{\sum_j T_j} \times 100\% \quad \text{where } t_{ij} \text{ is the } i^{\text{th}} \text{ duration of EtAA concentration}$$

maintained within the acceptable limit during the  $j^{\text{th}}$  steady state, and  $T_j$  is the total duration of the  $j^{\text{th}}$  steady state.  $I_{ij}$  is an indicator for whether EtAA is maintained within the acceptable limit of  $i^{\text{th}}$  duration in  $j^{\text{th}}$  steady state, which is

$$I = \begin{cases} 1 & \begin{array}{l} \text{if Desflurane and } \Delta EtAA \leq \max(0.6\%, 5\%X \text{ steady state EtAA}) \\ \text{if Sevoflurane and } \Delta EtAA \leq \max(0.2\%, 5\%X \text{ steady state EtAA}) \\ \text{if Isoflurane and } \Delta EtAA \leq \max(0.1\%, 5\%X \text{ steady state EtAA}) \end{array} \\ 0 & \text{otherwise} \end{cases}$$

$\Delta EtAA$  is the absolute difference between measured EtAA concentrations and steady state EtAA concentration.

(2) Percent duration without large deviation of  $EtO_2$ :

Percent duration of  $EtO_2$  concentration during steady state maintained within the acceptable limit, which is defined as 5% v/v. This definition is similar to that of the EtAA, except that the acceptable limit is set as 5% v/v.

**NOTE:** The steady state concentration is based on extraction algorithm for both Et Control and Control arms as well as based on the clinician's recorded target values for the Control Arm and the set target values for the Et Control Arm.

These two primary endpoints, along with the secondary efficacy endpoints (response time, setting time, overshoot amount), are chosen to assess the capability of Et Control in achieving and maintaining the end tidal concentration of anesthetic agent and oxygen.

This study is designed to demonstrate that Et Control is non-inferior to the control device in maintaining end tidal anesthetic agent (EtAA) and end tidal oxygen ( $EtO_2$ ) concentrations by a margin of 5%.

The hypotheses for the primary endpoints are:

$$H_0: \mu_{\text{et}} - \mu_{\text{con}} < -5\% \text{ vs } H_1: \mu_{\text{et}} - \mu_{\text{con}} \geq -5\%$$

for both EtAA and  $EtO_2$ , where  $\mu_{\text{et}}$  is the average percent duration of Et Control with EtAA and  $EtO_2$  maintained within the acceptable range, and  $\mu_{\text{con}}$  is the average percent duration of control device with EtAA and  $EtO_2$  maintained within the acceptable range.

### 3.4.2 Secondary Endpoint:

(1) Efficacy

- a. Response time: time to reach 90% of the desired change in EtAA and  $EtO_2$  steady state mean concentration

**Study Title:** Multi-site Anesthesia randomized controlled Study of End tidal control (Et Control) compared to conventional anesthesia Results (MASTER-Anesthesia Trial)  
**Study No:** 123.07-2015-GE5-0002

GE Healthcare

- b. Settling time: time to achieve the desired EtAA and EtO2 steady state mean concentration
- c. Overshoot amount of the desired EtAA and EtO2 from steady state mean concentration
- d. Accuracy of Et Control in maintaining EtAA and EtO2 control between user set target and steady state end tidal concentrations – For Et Control only. The accuracy measures include percent difference relative to the user set target and percent duration over the steady status with percent difference greater than 5%, 10%, and 15% of the user set target.

**NOTE:** *The response time, settling time, and overshoot amount data extraction will be done in two scenarios: 1) using the algorithmic determination of desired end-tidal concentration of anesthetic agent and oxygen for both arms (see [Appendix 2](#)), and 2) using the clinicians recorded target values of anesthetic agent and oxygen for the Control Arm and using the set target values for the Et Control arm.*

- (2) Safety
  - a. Adverse events (see definition under Section 10.2—[Adverse Event Definitions](#)) will be observed and recorded, the number of events will be counted, and comparison between groups will be performed.

### 3.4.3 Other Endpoints:

- (1) Usage of inhaled anesthetic agent;
- (2) Number of user interactions; AND
- (3) Time to discharge from the operating room (OR) (measured from the end of surgery [often defined as the procedure end time, last stitch, or placement of last bandage] to time of last breath).

## 4. DESIGN OF RESEARCH STUDY

### 4.1 Type of Research Study

This is a prospective, multi-site, single-blind, randomized, controlled clinical study of the investigational Et Control feature of the Aisys CS Anesthesia Machine.

### 4.2 Controls and Minimization of Bias

All reasonable attempts will be made to control and minimize bias during this study, including the following:

- Consecutive enrollment of subjects will be employed to limit selection bias.

**Study Title:** Multi-site Anesthesia randomized controlled Study of End tidal control (Et Control) compared to conventional anesthesia Results (MASTER-Anesthesia Trial)  
**Study No:** 123.07-2015-GE5-0002

GE Healthcare

- Subjects will be randomized in a single-blind method to either the Et Control Arm or the Control Arm.
- Subjects will be blinded to their assignment; however, given the nature of the use of the investigational Et Control option during a case, the clinicians and Investigators cannot be blinded to the subject groups.
- Quotas or stratification criteria will be employed to ensure equitable distributions of patients and thus reduce spectrum bias.
- Multiple sites will be used to provide a broader cross-section of the population of patients and clinical practices, and thus reduce spectrum bias

## 5. STUDY SUBJECTS

### 5.1 Number of Subjects

A total of 248 Subjects will be enrolled in the study, with approximately 124 subjects enrolled in each arm: Et Control Arm and Control Arm. A minimum of 15 subject cases is the target enrollment for each of the 3 anesthesia agents (Desflurane, Sevoflurane, and Isoflurane) per arm (*only one inhalation anesthetic agent may be used for each enrolled subject in the study arm*).

The study will be conducted at 4 hospitals (investigational sites) located within the United States. Each investigational site is to enroll a minimum of 30 to a maximum of 80 subjects with approximately 1:1 ratio for subject in the Et Control Arm and Control Arm.

Each Investigator will be performing a minimum of five (5) cases for each arm (Et Control and Control). In situations where the Investigator is unable to complete a minimum of 5 cases in each arm, a Sponsor exception may be obtained. Subjects will be randomized to the Et Control Arm or the Control Arm, and randomization will be stratified based on Investigator, subject's pre-existing hypertension status, and subject's ASA status.

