## 8. DATA ANALYSIS AND STATISTICS

### 8.1 Statistical Analysis Methods

#### 8.1.1 Sample Size Determination

This study is intended to demonstrate that Et Control is non-inferior to the control device in maintaining end tidal anesthetic agent (EtAA) and end tidal oxygen (EtO2) concentrations.

The primary efficacy endpoint is the weighted average per subject of percent duration of EtAA and EtO2 concentrations maintained within the acceptable range for a subject. The acceptable range is specific for each steady state. For EtAA, the acceptable range is defined as +/- the larger of 5% of the steady state concentration or 0.1% v/v for Iso, 0.2% v/v for Sev, 0.6% v/v for Des; and for EtO2, it is +/- 5% v/v. The duration of each steady state will be used as the weight when calculating the weighted average. For EtAA,

$$\text{PercentDuration} = \frac{\sum_j \sum_i t_{ij} I_{ij}}{\sum_j T_j} \times 100\% \quad \text{where } t_{ij} \text{ is the } i^{\text{th}} \text{ duration of EtAA concentration}$$

maintained within the acceptable limit during the  $j^{\text{th}}$  steady state, and  $T_j$  is the total duration of the  $j^{\text{th}}$  steady state.  $I_{ij}$  is an indicator for whether EtAA is maintained within the acceptable limit of  $i^{\text{th}}$  duration in  $j^{\text{th}}$  steady state, which is

$$I = \begin{cases} 1 & \begin{array}{l} \text{if Desflurane and } \Delta\text{EtAA} \leq \max(0.6\%, 5\%X \text{ steady state EtAA}) \\ \text{if Sevoflurane and } \Delta\text{EtAA} \leq \max(0.2\%, 5\%X \text{ steady state EtAA}) \\ \text{if Isoflurane and } \Delta\text{EtAA} \leq \max(0.1\%, 5\%X \text{ steady state EtAA}) \end{array} \\ 0 & \text{otherwise} \end{cases}$$

$\Delta\text{EtAA}$  is the absolute difference between measured EtAA concentrations and steady state EtAA concentration.

Similar definition is used for EtO2 except that acceptable limit is set as 5% v/v.

From the results of the feasibility study, the average percent duration of EtAA and EtO2 concentrations that exceeded the defined acceptable range for the Control Arm was about 13% and about 18%, respectively. In this study, the non-inferiority margin is set at 5% for both EtAA and EtO2, which is about 1/3 of the performance of the Control Arm, i.e., Et Control will be considered non-inferior to the control device if its performance is no worse than that of the control device by more than 5%.

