So the hypotheses on the primary endpoints are:

$$H_0: \mu_{\text{et}} - \mu_{\text{con}} < -5\% \text{ vs } H_1: \mu_{\text{et}} - \mu_{\text{con}} \geq -5\%$$

**Study Title:** Multi-site Anesthesia randomized controlled Study of End tidal control (Et Control) compared to conventional anesthesia Results (MASTER-Anesthesia Trial)  
**Study No:** 123.07-2015-GE5-0002

GE Healthcare

for both EtAA and EtO2, where  $\mu_{et}$  is the percent duration of Et Control with EtAA and EtO2 maintained within the acceptable range, and  $\mu_{con}$  is the percent duration of control device with EtAA and EtO2 maintained within the acceptable range.

Both null hypotheses have to be rejected for EtAA and EtO2 to conclude non-inferiority. So the alpha is set at 0.025 one-sided with no need for multiplicity adjustment, but the power for each hypothesis is set at 0.95 to have an overall power of 0.9 for the study. And the larger sample size calculated for EtAA and EtO2 will be the size of the study.

The results from the feasibility study on the weighted average of percent duration with EtAA and EtO2 maintained within the acceptable range is listed below. The difference between Et Control and control device is assumed to be 50% less than what was observed, and the larger standard deviation observed is used in sample size calculation using the 2-sample t-test method.

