**Table 8-1 – Sample Size Calculation**

Endpoint	Control device	EtControl (observed)	EtControl (expected)	Sample size per arm with 15% drop out	Sample size of the study
EtAA	87±16	94±16	90±16	124	248
EtO 2	81±19	98±19	89±19	68	136

So, on the basis of the above, the study will enroll approximately 248 subjects.

Superiority will be tested with no need for multiplicity adjustment, if non-inferiority is concluded. Superiority will be claimed for Et Control if EtAA is superior than the control, and EtO2 is non-inferior to the control. The significance level will be at 0.025 one-sided.

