### 8.1.2 Statistical Methods Overview

Data collected in this study will be presented using summary tables, data listings and graphs. Study endpoints and parameters will be summarized using descriptive statistics.

The descriptive statistics for continuous variables will include mean, standard deviation, median, Q1 and Q3, minimum, maximum, and sample size. Categorical variables will be described with counts, percentages, and sample size.

For comparison (between arms or against null values), categorical variables will be tested using appropriate contingency table analyses (exact or chi-square approximations), and continuous variables will be tested using Student's t-test or non-parametric methods, depending on variable distribution. P-values will be presented to three decimal places and p-values less than .001 will be presented as '<.001.'

**Study Title:** Multi-site Anesthesia randomized controlled Study of End tidal control (Et Control) compared to conventional anesthesia Results (MASTER-Anesthesia Trial)  
**Study No:** 123.07-2015-GES-0002

GE Healthcare

Subjects using different anesthetic agents will be pooled for analysis per the arm they are randomized. Separate analysis may be performed by anesthetic agent when pooling data across anesthetic agents is not appropriate.

No imputation will be performed for missing data unless specified otherwise.

A data extraction algorithm is used to identify periods of end tidal concentration measurement stability following setting changes (i.e. Steady States) during a case, as well as to measure response times, settling times, and overshoot amounts from these steady states in order to compare across arms. The extraction algorithm is not part of the statistical analysis, but provides the above-mentioned endpoints. (See Appendix 2 – Extraction algorithm for more information on the extraction algorithm.)

There will be two scenarios in defining a step change and steady state when performing the data extraction: 1) *using the data extraction algorithm to determine the desired end-tidal concentrations of anesthetic agent and oxygen for both arms* (See Appendix 2 – Extraction algorithm for more information on the extraction algorithm); 2) *using the clinicians recorded end tidal target values of anesthetic agent and oxygen for the Control arm, and the set target value for the Et Control arm.*

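### The EtAA limit depends on the anesthetic agent, but the intended agent is not declared before randomization, while a per-arm agent target runs with unblinded clinicians and a pooled, unadjusted t-test

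*Combined protocol and SAP*

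**What the plan says.** Sections 3.4.1 and 8.1.1 set the EtAA limit as the greater of 5% of the steady-state concentration and a fixed floor of 0.6% v/v for desflurane, 0.2% for sevoflurane or 0.1% for isoflurane. The EtO2 limit is 5% v/v for every agent.

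Section 5.1 sets the agent target: "A minimum of 15 subject cases is the target enrollment for each of the 3 anesthesia agents", per arm, with one agent per subject. It gives no mechanism for reaching it. Sections 5.1 and 6.1 stratify randomization by Investigator, hypertension status and ASA status only. Section 5.6.2 lets randomization take place up to 24 hours before induction. Section 4.2 says that "the clinicians and Investigators cannot be blinded to the subject groups". Neither the preoperative data list (Section 6.3.1) nor the schedule (Appendix 3) includes the intended inhaled agent.

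On analysis, Section 8.1.2 says "Subjects using different anesthetic agents will be pooled for analysis per the arm they are randomized". It adds that agents may be analyzed separately where pooling is not appropriate, without a criterion. Section 8.1.3 compares the arms by t-test and names no covariates. Agent is a covariate only in the imputation model of Section 8.3.

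**The concern.** Randomization balances what is fixed before allocation. In this plan the agent can be settled afterwards, by someone who knows the arm, and a target counted within each arm makes the arm relevant to that choice. If agents differ in how much time falls within their limits, a difference in agent mix carries straight into the pooled EtAA comparison. EtAA matters most here: it sets the sample size and alone decides the superiority claim. The pooled agent-usage comparison in Section 8.1.4.2 has the same exposure, to the extent that normalization does not remove differences between agents.

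This is hard to repair later. The agent actually used is a post-randomization variable, so adjusting for it is not a safe substitute for adjusting for an agent declared beforehand.

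**Working it through.** **1. The plan's sample size, which supplies the standard error used below.** Inputs from Section 8.1.1 and Table 8-1: "So the alpha is set at 0.025 one-sided with no need for multiplicity adjustment"; power 0.95 per hypothesis; margin 5 points; EtAA 87 versus an expected 90, SD 16; EtO2 81 versus 89, SD 19; 15% dropout; two-sample t-test.
- EtAA: distance to the margin 5 + 3 = 8, giving 105 per arm; 105/0.85 = 123.5, so 124.
- EtO2: distance 5 + 8 = 13, giving 57 per arm; 57/0.85 = 67.1, so 68.

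Both match Table 8-1. The sample size is not in question.

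**2. How far the EtAA limit depends on agent.** The MAC values are in footnote 1 of Section 2.1 (6.0, 2.1 and 1.15% v/v).

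| Agent | Floor / 1 MAC | 5% rule exceeds the floor only above |
|---|---|---|
| Desflurane | 0.6/6.0 = 10.0% | 0.6/0.05 = 12% v/v (2.0 MAC) |
| Sevoflurane | 0.2/2.1 = 9.5% | 0.2/0.05 = 4% v/v (1.9 MAC) |
| Isoflurane | 0.1/1.15 = 8.7% | 0.1/0.05 = 2% v/v (1.7 MAC) |

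Below those concentrations the agent alone fixes the limit. In MAC terms the limits are close but not equal.

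**3. What that could mean for in-range time.** The document gives no results by agent, so this is an illustration. Assume deviations are normal with the same SD σ in MAC units for all agents, with σ chosen so that the three-agent average equals a given value. In-range proportion = 2Φ(limit/σ) − 1.

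| Average in range | σ (MAC) | Des | Sev | Iso | Des − Iso |
|---|---|---|---|---|---|
| 87% | 0.0619 | 89.4 | 87.6 | 84.0 | 5.4 |
| 90% | 0.0569 | 92.1 | 90.6 | 87.3 | 4.8 |
| 94% | 0.0497 | 95.6 | 94.5 | 92.0 | 3.6 |

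**4. Bias = agent difference × between-arm gap in agent share** (share moved between desflurane and isoflurane).
- 10-point gap: 0.10 × 3.6 = 0.36 to 0.10 × 5.4 = 0.54, or 7% to 11% of the margin.
- 30-point gap: 0.30 × 3.6 = 1.08 to 0.30 × 5.4 = 1.62, or 22% to 32% of the margin.

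**5. Effect on the non-inferiority test if the bias favored Et Control.** SE = 16 × √(2/105) = 2.21. With a true difference exactly at the margin, one-sided type I error (noncentral t) rises from 0.025 to 0.041 for a 0.5-point bias and to 0.100 for a 1.5-point bias. A bias the other way would make the test conservative.

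**6. Chance, or choice?** With 124 per arm, the SD of a chance gap in an agent's share is √(2p(1−p)/124): 3.8 points at p = 10% and 6.0 at p = 33%. A 30-point gap would therefore need arm-dependent choice.

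**7. Would the target be met without steering?** For an agent's natural share p (assumed), the binomial probability of at least 15 in both arms of 124 is 0.07 at 10%, 0.28 at 12%, 0.72 at 15% and 0.985 at 20%. For a seldom-used agent, ordinary practice would usually miss the target.

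**The case against.** The case against has real force.

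- **One co-primary only.** A reader might infer that both primary endpoints are affected through their limits. They are not: the EtO2 limit is the same for all agents.
- **The floors are roughly scaled to potency.** At 10.0%, 9.5% and 8.7% of 1 MAC they are close enough to make pooling reasonable. A larger figure is tempting: if agents differed by 10 points in in-range time, a 10-point mix gap would give 1 point, or 20% of the margin. Nothing in the document supplies that 10-point difference, and under the assumptions above the unequal limits give about half of it.
- **Steering is not documented.** A reader might infer that the plan has clinicians choose the agent by arm. It does not say when the agent is chosen. It calls the 15 a target, and Section 6.1.1 leaves dosage decisions to normal practice. Stratifying by Investigator balances habitual preference between arms, though it does not stop arm-dependent choice by one investigator.
- **Agent usage has safeguards.** Section 8.1.4.2 normalizes usage before pooling and also compares usage for each agent, so it would be wrong to call the usage claim unprotected.
- **Imbalance would show.** Section 8.1.9 summarizes delivered concentrations by agent and arm, and Section 8.1.2 permits analysis by agent.

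One further mechanism remains open. Appendix 2 defines agent stability by a single rate, 0.2% v/v per minute, which is 0.033, 0.095 and 0.174 MAC per minute for desflurane, sevoflurane and isoflurane. This could add dependence on agent, but its effect has not been quantified and no conclusion here rests on it.

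What survives is narrower: nothing in the document fixes the intended agent before allocation, and the primary comparison would display an arm-dependent agent mix without correcting for it.

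**Conclusion.** The point holds as an open risk in the EtAA comparison that is cheap to reduce. It does not show that the comparison is biased, and it does not undermine the trial's validity. Direction is unknown and size depends on assumptions: about 0.4 to 0.5 point for a 10-point difference in agent mix, and about 1.1 to 1.6 points for a 30-point difference, against the 5-point margin. These figures assume normal deviations with equal SD in MAC units, average in-range time of 87% to 94%, and a shift between desflurane and isoflurane, the pair furthest apart. For desflurane versus sevoflurane the difference at 87% is only 89.4 − 87.6 = 1.8 points, or about 0.2 point for a 10-point gap. The randomization-system specification and the case report forms are not part of the document, so planned agent may be captured there; the protocol does not say.

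**What to change.** 1. Enter the planned agent in the IVRS/IWRS before the allocation is shown.
2. Count the 15-per-agent target on planned agent at enrollment, so that filling a cell cannot depend on the arm.
3. Include planned agent as a covariate in the EtAA primary analysis and in the pooled normalized agent-usage analysis. Keep the usage comparison for each agent in Section 8.1.4.2.
4. Report departures from planned agent by arm.

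The covariate handles imbalance in planned agent. It does not undo a switch made after allocation, which is why steps 2 and 4 are needed.

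Adding agent as a fourth stratification factor is not practical. With at least 10 cases per investigator there could be up to 24 investigators (an assumed upper bound), so 24 × 2 × 3 = 144 strata would become 432 for 248 subjects.

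The cost is one field, a slightly earlier statement of the intended agent, one covariate, and less direct control over how many subjects actually receive each agent in each arm. The sample size stays at 124 per arm, and clinicians remain free to use whichever agent they judge appropriate.
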